## **Site Operations Manual (SOM)**

A Site Operations Manual (SOM) accompanies this protocol, providing the operational details for study procedures. Note: The SOM will not be a part of the Clinical Study Report.

### List of abbreviations

AE	adverse event
ALT	alanine aminotransferase
ANCOVA	analysis of covariance
APA	American Psychological Association
AR(1)	first-order autoregressive
AST	aspartate aminotransferase
AUC	Area Under the Curve
AUCinf	Area Under the Curve from time zero to infinity
AUClast	area under the curve from time zero to time of last measurable concentration

### Commercially Confidential Information

BP	Blood Pressure
BRMS	Bech-Rafaelsen Melancholia Scale
BUN	blood urea nitrogen
C-SSRS	Columbia Suicide Severity Rating Scale
CADSS	Clinical-Administered Dissociative States Scale
CFR	U.S. Code of Federal Regulations
CGI	Clinical Global Impression
CGI-I	Clinical Global Impression of Improvement
CGI-S	Clinical Global Impression of Severity
CK	creatinine kinase
CL	apparent total body clearance of the drug from plasma
cm	centimeter(s)
Cmax	maximum plasma drug concentration
CMO&PS	Chief Medical Office & Patient Safety
CNS	Central Nervous System
CO 2	carbon dioxide
CRA	Compliance and Regulatory Affairs
CRF	Case Report/Record Form (paper or electronic)
CRO	Contract Research Organization

### Commercially Confidential Information

CSR	Clinical study report
CTC	Common Toxicity Criteria
CV	coefficient of variation
DAE	Dissociative adverse event
DAR	Dose Administration Record
DDE	Direct Data Entry
DES	Dissociative Experiences Scale
DNA	Deoxyribonucleic Acid
DSM-5	Diagnostic and Statistical Manual of Mental Disorders, Fifth Edition
ECG	Electrocardiogram
eCRF	electronic Case Report Form

EDC	Electronic Data Capture
EMA	European Medicines Agency
EU	Europe
FAS	Full Analysis Set
FIH	First in Human
FSH	Follicle Stimulating Hormone
GASE	Generic Assessment of Side Effects
GCP	Good Clinical Practice
GCS	Global Clinical Supply
GGT	Gamma-glutamyl transferase
GLP	Good Laboratory Practice
h	Hour
HAM-A	Hamilton Anxiety Rating Scale
HIV	human immunodeficiency virus
hsCRP	High Sensitivity C-Reactive Protein
IB	Investigator's Brochure
ICF	Informed Consent Form
ICH	International Conference on Harmonization of Technical Requirements for Registration of Pharmaceuticals for Human Use
IEC	Independent Ethics Committee
IL	Interleukin
IN	Investigator Notification
IRB	Institutional Review Board
IRT	Interactive Response Technology
ITT	Intent-to-Treat
IUD	intrauterine device
IUS	intrauterine system
kg	killogram(s)
KMDRS	Koukopoulos Mixed Depression Rating Scale
KR	Kenward-Roger
LC-MS/MS	Liquid Chromatography-tandem Mass Spectrometry
LDH	lactate dehydrogenase

Commercially Confidential Information

MADRS	Montgomery Asberg Depression Rating Scale
MDD	Major Depressive Disorder
MDE	Major Depressive Episode
MedDRA	Medical dictionary for regulatory activities
mg	milligram(s)
mL	milliliter(s)
MMDC	Melancholia and Mixed Depression Diagnostic Checklist
MMRM	Mixed-effects Model for Repeated Measures
MTI	Maudsley Treatment Inventory

NIRT	Novartis Interactive Response Technology
NMDA	N-methyl-D-aspartate
NOEL	No Observable Effect Level
PD	pharmacodynamic(s)
PHQ	Patient Health Questionnaire
PK	pharmacokinetic(s)
PPS	per protocol set
QMS	Quality Management System
QTcB	QT interval corrected by Bazett's formula
QTcF	QT interval corrected by Fridericia's formula
RBC	red blood cell(s)
RoW	Rest of World
SAE	serious adverse event
SCID-5(-RV)	Structured Clinical Interview for DSM-5 (Research Version)
SD	standard deviation
SMPI	Sydney Melancholia Prototype Index
SMQ	Standardized MedDRA Query
SOM	Site Operations Manual
STS	Suicidality Tracking Scale
SUSAR	Suspected Unexpected Serious Adverse Reactions
T1/2	Elimination half-life
Tmax	time to reach maximum plasma concentration
TRD	Treatment-Resistant Depression
TSH	thyroid-stimulating hormone
ULQ	Upper Limit of Quantification
UN	unstructured
US	United States
Vz	apparent volume of distribution during terminal phase
WBC	white blood cell(s)
WHO	World Health Organization
WOC	Withdrawal of consent
β-hCG	Beta-Human Chorionic Gonadotropin

## Glossary of terms

Assessment	A procedure used to generate data required by the study
Biologic Samples	A biological specimen including, for example, blood (plasma, serum), saliva, tissue, urine, stool, etc. taken from a study subject
Cohort	A specific group of subjects fulfilling certain criteria
Control drug	A study drug (active or placebo) used as a comparator to reduce assessment bias, preserve blinding of investigational drug, assess internal study validity, and/or evaluate comparative effects of the investigational drug
Dosage	Dose of the study treatment given to the subject in a time unit (e.g. 100 mg once a day, 75 mg twice a day)
Electronic Data Capture (EDC)	Electronic data capture (EDC) is the electronic acquisition of clinical study data using data collection systems, such as Web-based applications, interactive voice response systems and clinical laboratory interfaces. EDC includes the use of Electronic Case Report Forms (eCRFs) which are used to capture data transcribed from paper source forms used at the point of care
End of the clinical trial	The end of the clinical trial is defined as the last visit of the last subject or at a later point in time as defined by the protocol
Enrollment	Point/time of subject entry into the study at which informed consent must be obtained
Epoch	Interval of time in the planned conduct of a study. An epoch is associated with a purpose (e.g. screening, randomization, treatment, follow-up) which applies across all arms of a study.
eSource	eSource Direct Data Entry (DDE) refers to the capture of clinical study data electronically, at the point of care. eSource combines source documents and case report forms (eCRFs) into one application, allowing for the real time collection of clinical trial information to sponsors and other oversight authorities, as appropriate.
Healthy volunteer	A person with no known significant health problems who volunteers to be a study participant
Investigational drug/treatment	The drug whose properties are being tested in the study
Medication number	A unique identifier on the label of medication kits
Part	A single component of a study which contains different objectives or populations within that single study. Common parts within a study are: a single dose part and a multiple dose part, or a part in patients with established disease and in those with newly-diagnosed disease.
Patient	An individual with the condition of interest for the study
Personal data	Subject information collected by the Investigator that is transferred to Novartis for the purpose of the clinical trial. This data includes subject identifier information, study information and biological samples
Randomization number	A unique identifier assigned to each randomized subject
Screen Failure	A subject who did not meet one or more criteria that were required for participation in the study
Source Data/Document	Source data refers to the initial record, document, or primary location from where data comes. The data source can be a database, a dataset, a spreadsheet or even hard-coded data, such as paper or eSource

Study treatment	Any single drug or combination of drugs or intervention administered to the subject as part of the required study procedures
Study treatment discontinuation	When the subject permanently stops taking any of the study drug(s) prior to the defined study treatment completion date (if any) for any reason; may or may not also be the point/time of study discontinuation
Subject	A trial participant (can be a healthy volunteer or a patient)
Subject number	A unique number assigned to each subject upon signing the informed consent. This number is the definitive, unique identifier for the subject and should be used to identify the subject throughout the study for all data collected, sample labels, etc.
Treatment arm/group	A treatment arm/group defines the dose and regimen or the combination, and may consist of 1 or more cohorts.
Variable	A measured value or assessed response that is determined in specific assessments and used in data analysis to evaluate the drug being tested in the study
Withdrawal of consent (WoC)	Withdrawal of consent from the study occurs only when a subject does not want to participate in the study any longer and does not allow any further collection of personal data

Commercially Confidential Information

Commercially Confidential Information

Commercially Confidential Information

## Protocol summary

Protocol number	CMIJ821X2201
Full Title	A multi-center, randomized, subject and investigator-blinded, placebo-controlled, active comparator, parallel-group proof of concept study to evaluate the efficacy, safety, tolerability, and pharmacokinetics of MIJ821 in patients with treatment-resistant depression
Brief title	Study of efficacy and safety of MIJ821 in treatment-resistant depression patients.
Sponsor and Clinical Phase	Novartis
Investigation type	Drug
Study type	Interventional
Purpose and rationale	
The main purpose of this non-confirmatory study is to evaluate the clinical responses of MIJ821 in patients suffering from treatment-resistant depression assessed by the Montgomery Åsberg Depression Rating Scale (Montgomery and Asberg 1979).
 
Furthermore it is expected that this study will guide the future clinical trials with MIJ821 in treatment of resistant depression.

Primary Objective(s)	The primary objective of this study is to assess the efficacy of MIJ821 in treatment-resistant depression at 24 hours after the start of infusion. The measure will be conducted through MADRS total score, 24 hours after the start of first infusion compared to the baseline assessment.
Secondary Objectives	
To assess the efficacy of MIJ821 in treatment-resistant depression by 1) evaluating the percentage of treatment response (>50% improvement in MADRS) at 24 hours, 48 hours (if applicable) and 6 weeks after the start of first infusion 2) evaluating the percentage of remission (MADRS <7) at 24 hours, 48 hours (if applicable) and 6 weeks after the start of first infusion; 3) evaluating the CGI-I and CGI-S scores at 24 hours, 48 hours (if applicable), and 6 weeks after the start of first infusion.
 
To assess the impact of MIJ821 on suicidality.
 
To assess the MIJ821 pharmacokinetics in plasma.
 
To assess the most effective dose and dosing regimen.
 
To assess the safety and tolerability of weekly and bi-weekly infusions of MIJ821.
 
To assess the efficacy in melancholic subtype of depression.
 
To assess the risk of mania induction.
 
To assess the efficacy of MIJ821 for mixed mood symptoms.
 
To assess the efficacy of MIJ821 for anxiety symptoms.
 
To assess the impact of mixed mood symptoms, melancholia, and anxiety as predictors of treatment response to MIJ821.

Study design	This is a multi-center, randomized, parallel group, active comparator, placebo-controlled study. The study will enroll approximately 66 subjects presenting with Treatment-Resistant Depression. The study consists of a screening and baseline period (D-28 to D-1), a treatment period (D1 to D36) and a 5 week follow-up period with an end of study visit on Day 71. The maximum duration of the study including screening is approximately 14 weeks.
Population	Male and female subjects, 18 to 65 years (inclusive), diagnosed with Treatment-Resistant Depression. Eligible subjects may come from either an inpatient or outpatient treatment setting.
Key Inclusion criteria	
 
• Signed informed consent must be obtained prior to participation in the study.
 
• Male and female subjects, 18 to 65 years of age (inclusive) at screening.
 
• Subject is in a DSM-5 defined major depressive episode at the time of screening
 
• Subject obtains a Montgomery-Åsberg Depression Rating Scale (MADRS) score <math>\geq 24</math> at screening and baseline
 
• Failure to response to two or more prior antidepressant treatments, where two failed treatments are of two different antidepressants, with adequate dose and duration (<math>\geq 8</math> weeks duration, doses defined per agent) for the current or prior major depressive episode, as identified by the Maudsley Treatment Inventory, and prior psychiatric history, assessed by the investigator, and further documented by medical records and/or third party report (family, friends, clinician-treaters) where available
 
• At least one prior clinical depressive episode (recurrent major depressive disorder), as identified by prior psychiatric history assessed by the investigator, and further documented by medical records and third party report (family, friends, clinician-treaters) where available.
 

Key Exclusion criteria	
 
• Any current diagnosis of bipolar disorder, schizophrenia, or schizoaffective disorder.
 
• Current alcohol or substance use disorder (including marijuana and prescribed amphetamine) meeting DSM-5 criteria, within the past month at baseline. Nicotine and caffeine use disorders are not considered as exclusionary substances.
 
• Prior suicidality caused by or associated with ketamine, as identified by prior psychiatric history assessed by the investigator, and augmented by medical records and third party report (family, friends, clinician-treaters) where available.
 
• Acute serious and/or imminent suicidal ideation and/or intent within the prior 2 weeks, or any suicide attempt within the prior 4 weeks at screening. Mild to moderate suicidal ideation, using the Sheehan Suicidal Ideation Scale and not meeting the above definition, is not an exclusion criterion.
 
• Use of other investigational drugs within 30 days or 5 half-lives of randomization, whichever was longer; or longer if required by local regulations.
 
• Current pregnancy or lactation.
 
• Positive HIV, Hepatitis B or C test.
 
• Resting QTcF <math>\geq 450</math> msec (male) or <math>\geq 460</math> msec (female) at pre-treatment baseline.
 

Study treatment	
Patients who meet the eligibility criteria at screening and baseline will be randomized to one of the six treatment arms in the European countries (only five arms in the USA as there is no ketamine arm)
 
Commercially Confidential Information

Efficacy assessments	

• Montgomery Åsberg Depression Rating Scale at 24 hours post-dose

• % treatment response (>50% improvement in MADRS) at 24 hours, 48 hours (if applicable), and 6 weeks after the start of first infusion

• % treatment remission (MADRS<7) at 24 hours, 48 hours (if applicable), and 6 weeks after the start of first infusion

• CGI-S and CGI-I scores at 24 hours, 48 hours (if applicable), and 6 weeks after the start of first infusion Sheehan Suicidality Tracking Scale score changes from baseline at 24 hours, 48 hours (if applicable), and 6 weeks after the start of first infusion

• Montgomery Åsberg Depression Rating Scale score at 6 weeks after the start of first infusion

Other assessments	
Commercially Confidential Information

Pharmacokinetic assessments	
MIJ821 pharmacokinetics in plasma

Key safety assessments	
Adverse event monitoring, Physical examinations, Monitoring of laboratory markers in blood and urine, ECGs.

Data analysis	
The change from baseline in the total MADRS score at 24 hours after single dose administration will be analyzed using an analysis of covariance (ANCOVA) model with treatment as a group factor and baseline MADRS score as a covariate.
 
Commercially Confidential Information

Key words	
Treatment-Resistant Depression; Major Depressive Episode; Major Depressive Disorder

## 1 Introduction

### 1.1 Background

Treatment-resistant depression (TRD) is defined as a failure to respond to at least two different antidepressants for a period longer than 4-6 weeks at the maximum recommended dose (Sackeim 2001). One-third or more of patients suffering from unipolar depressive illness, defined in DSM-5 as major depressive disorder (MDD), fail to respond acutely to antidepressant treatment of adequate dose and duration (Rush et al 2006). Even more subjects, the majority in fact, fail to maintain long-term response to standard antidepressants (Rush et al 2006). Further, suicide is a major harm with depressive illness, with depression being present in the vast majority of persons who commit suicide (Isometsä 2001). Most antidepressants have a few weeks delay in symptom benefit, during which time individuals can be at suicidal risk.

Commercially Confidential Information

Ketamine, which is a NMDA receptor antagonist, has been shown to be effective in TRD in off-label research, but is limited by psychotomimetic side effects (Katalinic et al 2013; Browne and Lucki 2013). Further ketamine has been shown to be rapid-acting and reduce suicidality (Katalinic et al 2013). The efficacy of ketamine provides the rationale for targeting NMDA receptor inhibition as a rapid-onset antidepressant mechanism.

Commercially Confidential Information

### 1.2 Purpose

The main purpose of this non-confirmatory study is to evaluate the clinical responses of MIJ821 in subjects suffering from treatment-resistant depression assessed by the Montgomery Åsberg Depression Rating Scale (Montgomery and Asberg 1979), a validated and widely employed method in depression trials.

Furthermore, it is expected that this study will guide the future clinical trials with MIJ821 in patients with treatment resistant depression.

## 2 Objectives and endpoints

**Table 2-1 Objectives and related endpoints**

Objective(s)	Endpoint(s)
Primary objective(s)	Endpoint(s) for primary objective(s)

 
To assess efficacy of MIJ821 in treatment-resistant depression.
 
	
 
Montgomery Asberg Depression Rating Scale total score at 24 hours after the start of the infusion compared to the baseline assessment.
 

Secondary objective(s)	Endpoint(s) for secondary objective(s)

 
To assess risk of mania induction.
 
To assess efficacy in the melancholic subtype of depression.
 
To assess safety and tolerability, especially dissociative side effects.
 
To assess most effective dose and dosing regimen.
 
To assess MIJ821 pharmacokinetics in plasma.
 
To assess impact of MIJ821 on suicidality.
 
To assess efficacy of MIJ821 on measures of response and remission
 
To assess efficacy of MIJ821 for mixed mood symptoms.
 
To assess efficacy of MIJ821 for anxiety symptoms.
 
	
 
Young Mania Rating Scale at 24 hours, 48 hours (if applicable) and 6 weeks post-dose.
 
Bech-Rafaelsen Melancholia and CORE scale change from baseline to 24 hours, 48 hours (if applicable) and 6 weeks post-dose.
 
Incidence of adverse event Dissociative rating scales (Clinician-Administered Dissociative States Scale, and Dissociative Experiences Scale) change from baseline to 24 hours, 48 hours (if applicable) and 6 weeks post-dose.
 
Montgomery Asberg Depression Rating Scale score at 6 weeks.
 
PK properties of MIJ821 in plasma described by AUClast, AUC0-24h, Cmax, Tmax (parameters not limited)
 
Sheehan Suicidality Tracking Scale changes from baseline at 24 hours, 48 hours (if applicable), and 6 weeks after the start of first infusion.
 
% treatment response (>50% improvement in MADRS) at 24 hours, 48 hours (if applicable), and 6 weeks after the start of first infusion. % treatment remission (MADRS<7) at 24 hours, 48 hours (if applicable), and 6 weeks after the start of first infusion CGI-S and CGI-I scores at 24 hours, 48 hours (if applicable), and 6 weeks after the start of first infusion
 
Koukopoulos Mixed Depression Rating Scale change from baseline to 24 hours, 48 hours, and 6 weeks after the start of first infusion.
 
Hamilton Anxiety Scale change from baseline to 24 hours, 48 hours (if applicable), and 6 weeks after the start of first infusion
 

Objective(s)	Endpoint(s)


To assess impact of mixed mood symptoms, melancholia, and anxiety as predictors of treatment response to MIJ821.

	

Regression model effect sizes (odds ratios) for Hamilton Anxiety Scale, Bech-Rafaelsen Melancholia Scale, and Koukopoulos Mixed Depression Rating Scale as predictors, with MADRS treatment response as outcome, at 24 hours, 48 hours (if applicable), and 6 weeks after the start of first infusion.

Exploratory objective(s)	Endpoint(s) for exploratory objective(s)

Commercially Confidential Information

### **3 Study design**

This is a non-confirmatory, multi-center, 6-treatment arm in the European countries and 5-treatment arm in the USA (no ketamine arm), randomized, subject and investigator blinded, parallel group, placebo controlled study in treatment-resistant depression patients. The study will randomize approximately 66 Subjects and while the study design utilizes an outpatient visit schedule, the study allows for the inclusion of subjects seeking treatment for their disease from both an 'inpatient' or 'outpatient' clinic setting.

A screening period of maximum 4 weeks will be used to assess eligibility. Patients who meet the eligibility criteria at screening will proceed to baseline evaluations on Day-1 or Day 1. All baseline safety evaluation results must be available prior to randomization. At the baseline visit, eligible subjects will be randomized to one of the treatment arms. Randomized subjects will enter a 36- day treatment period, receiving at each treatment visit, a 40-minute infusion with a safety observation period of 2-4 hours (i.e. a minimum of 2 hours) post the start of

infusion. If the subject reports no dissociative symptoms and no suicidal symptoms, the subject will be allowed to leave the clinical treatment setting. Visits to assess efficacy and safety are scheduled at 24 hours, 48 hours (if applicable) and every week during the treatment period. If 48 hour visit (V103) is conducted, then all assessments should be completed. The assessment to address the primary objective will be performed at 24 hour post-dose. Safety assessments will include physical examinations, ECGs, vital signs, standard clinical laboratory evaluations (hematology, blood chemistry, and urinalysis), adverse event and serious adverse event monitoring. At the conclusion of the treatment period (Day 1 - Day 36), subjects will enter a 5-week follow up period consisting of two follow visits approximately 1 week (Day 43) and 3 weeks (Day 57) after the last study drug administration and an end of study completion visit (Day 71) The total duration for each subject in the study is maximum 14-weeks including screening and baseline. No interim analysis is planned. The study design is summarized in [Figure 3-1](#) below for the European countries (same study design without the ketamine arm in the USA).

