#### **4.5 Risks and benefits**

There is no expected benefit for subjects participating in the study. However, in instances of documented TRD, participants may benefit from receiving effective antidepressant therapy to treat the MDD.

The risks of participating in the study include those identified in the clinical studies with MIJ821, those associated with IV infusion and those associated with blood sampling. The risk to subjects in this trial may be minimized by compliance with the eligibility criteria, specific procedures done by qualified personnel, study stopping rules as well as close clinical monitoring.

Subjects will be observed for 2-4 hours (i.e. a minimum of 2 hours) after the start of infusion. If they have no dissociative symptoms and no suicidal symptoms after the observation period, they can leave the clinical treatment setting. If investigators judge that subjects have any dissociative symptoms, subjects will be monitored in the clinic until the dissociative symptoms resolve and/or extended stay overnight, or longer based on investigator judgment. If suicidal symptoms are present to a moderate to severe degree, either based on rating scales or investigator judgment, and such symptoms persist throughout the above 2-4 hours monitoring period, investigators may consider extending stay of subjects at least overnight. If suicidal symptoms are mild, either based on rating scales or investigator judgment, the investigator's judgment can be used to allow the subject to leave the clinical setting, but in that case arrangements should be made such that family members or friends are present with the subject for at least 24 hours. If such arrangements cannot be made, the subject may have extended stay at least overnight. If needed, an additional overnight stay beyond the first infusion's baseline and V101 is permissible.

Women of child bearing potential and sexually active males must be informed that taking the study treatment may involve unknown risks to the fetus if pregnancy were to occur during the study, and agree that in order to participate in the study they must adhere to the contraception requirements outlined in the exclusion criteria. If there is any question that the subject will not reliably comply, he/she should not be entered or continue in the study.

Sexually active males must be informed of the requirement to wear a condom for the following reasons:

- Prevent pregnancy in a female partner AND

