- Present delivery of investigational drug via seminal fluid to their partner as study treatment may involve unknown risks to the fetus if pregnancy were to occur.

Commercially Confidential Information

Commercially Confidential Information

Given that MIJ821 may impair the mental or physical abilities required for the performance of dangerous potential tasks such as driving a car or operating machinery, subjects should be advised about these potential risks. If the subject is feeling drunk or dizzy or if he/she experiences visual disturbances, hallucinations, or euphoric mood, then the subjects should not drive, use machines or perform any other tasks that require his/her attention and good coordination. In that case, the subject should be hospitalized until resolution of these events. These judgments will be made by the investigators, not the subjects.

In general, hypersensitivity or infusion reaction can manifest with itching, flushing, headache, nausea, vomiting, hypotension, urticaria, bronchospasm, or angioedema. In the event of a hypersensitivity reaction, stop the infusion immediately.

Subjects participating to the MIJ821X2201 study will be provided with a subject information card that they would carry with them at all time and as long as they are treated with MIJ821 or ketamine. This card will warn of potential interaction with CYP3A4, CYP2B6, CYP2C8, CYP2C19, or CYP2D6 inducers or inhibitors and should be presented to every physician/healthcare provider the subject may consult to inform them about potential drug interactions. It is also important that the subject is asked to contact his/her study doctor to inform him/her of his/her status as well as to discuss any treatment recommendations. As a general precaution with all investigational drugs, sites should have the capacity of managing acute hypersensitivity reactions (or similar emergency situations) or be prepared to transfer the subject urgently, should these reactions emerge.

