Benefits of ketamine have been shown for rapid improvement of depressive symptoms within 1-2 days, which persists up to 3-4 weeks after one dose. This improvement has been shown mainly with intravenous infusion of 0.5 mg/kg ketamine over 40 minutes ([Katalinic et al 2013](#)). Two open-studies ([Price et al 2009](#), [Thakurta et al 2012](#)) also have suggested that ketamine may be an appropriate treatment to rapidly reduce acute suicide risk in depressed patients. Benefits have been shown also recently with intranasal administration of esketamine. These benefits occur for acute depressive symptoms, and have not been studied or proven for long-term or maintenance administration. The amount of benefit seen acutely meets or exceeds the effect sizes seen with standard antidepressants. Some studies report such benefit in treatment-resistant depression, with patients who have failed multiple prior antidepressant trials. Such benefit has been seen with both bipolar and unipolar depression.

Most of the research conducted using subanaesthetic doses of ketamine has shown psychotomimetic and neuropsychological adverse effects: general psychiatric symptoms, agitation, dissociative symptoms and manic symptoms. These effects have mostly been restricted to the time of administration, disappearing completely by 60 minutes afterward. Other adverse events experienced by patients include feelings of intoxication and lowered inhibitions, confusions, decreased concentration and perceptual disturbances. Most of these

impairments were only apparent during the infusions, and none persisted longer than 2 hours after the beginning of the infusions.

There have been not many significant physical adverse event reported in studies of low-dose ketamine (used as an antidepressant) to date. Some studies have reported a variety of non-permanent physical effects such as light-headedness, headache, nausea, diplopia, drowsiness and dizziness. These symptoms tend to be benign and again limited to the period of the infusion or for a short time following.

Depression trials investigating subanaesthetic doses of ketamine consistently report transient elevations in blood pressure and heart rate during the period of infusion and for up to 80 minutes after dosing.

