There have been a number of case reports that have linked repeated ketamine use to urinary tract problems. These cases have mainly been reported in the context of recreational ketamine abuse (where use is chronic, doses are high, and comorbidity with other substance use is common).

Finally, there are concerns about the potential for dependence through long-term or repetitive ketamine use. However, low-dose usage in a medical setting is less likely to produce tolerance ([Katalinic et al 2013](#)).

The above risks will be minimized in this trial by clinical observation during and for 2-4 hours (i.e. a minimum of 2 hours) after the start of infusion period, as well as extended stay if needed based on clinical judgment at any point during the study. If severe dissociative, psychotic, suicidal, or agitated symptoms emerge, clinician-researchers will hospitalize research subjects until those clinical adverse events are resolved. If they persist, or based on clinician-researcher judgment or patient preference, those subjects can be dropped from the study as well at any time. Certain benzodiazepines, specifically lorazepam or alprazolam (as authorized by country), administration also is allowed in the study, within dosage limitations, to manage such possible agitation-related effects of ketamine.

The risk of collecting blood may include fainting, pain and/or bruising: rarely, these may be a small blood clot or infection at the site of the needle puncture. The risks with an IV infusion may include pain, swelling, redness or infection at the injection site. The risk is mitigated by selecting professional staff from the clinic experienced in making this type of infusion.

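### Protocol Section 3 lets the subject's own report decide release after infusion, while Section 4.5 keeps anyone the investigator judges dissociative; Section 3 needs one corrected sentence

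*Protocol*

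**What the plan says.** Section 3 of the protocol gives each treatment visit a 40-minute infusion, followed by observation for 2 to 4 hours from the start of infusion (at least 2 hours). It then states: "If the subject reports no dissociative symptoms and no suicidal symptoms, the subject will be allowed to leave the clinical treatment setting". It names no investigator judgment or rating scale, and it does not refer to Section 4.5.

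Section 4.5 covers the same observation period in more detail:

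- Its general release sentence depends on whether subjects *have* symptoms, not on whether they report them.
- For dissociation: "If investigators judge that subjects have any dissociative symptoms, subjects will be monitored in the clinic until the dissociative symptoms resolve", with an overnight or longer stay at the investigator's discretion.
- For moderate to severe suicidal symptoms that persist through observation: "investigators may consider extending stay of subjects at least overnight".
- For mild suicidal symptoms, the investigator's "judgment can be used to allow the subject to leave the clinical setting", with relatives or friends to be present for at least 24 hours.
- For dizziness, a feeling of drunkenness, visual disturbance, hallucination or euphoria: "In that case, the subject should be hospitalized until resolution of these events", and "These judgments will be made by the investigators, not the subjects".
- In its risk-minimization paragraph, the protocol relies on observation "as well as extended stay if needed based on clinical judgment at any point during the study" and requires clinicians to hospitalize subjects with severe dissociative, psychotic, suicidal or agitated symptoms.

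Section 10.1.1 makes the investigator responsible for the safety of each subject.

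**The concern.** A release rule that rests on self-report is weakest for the symptom it is meant to catch, because a dissociated subject may not recognize or volunteer the state. If staff take the rule from Section 3, a subject whom they judge dissociated may leave because that subject reports nothing. Section 4.5 requires the same subject to stay. A protocol should not give both instructions, least of all on dissociation, which the secondary objectives in Section 2 single out among the side effects.

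What is at stake is subject safety at discharge, not inference. No estimate, error rate or treatment comparison depends on this sentence.

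**Working it through.** No sample size, power or error rate is involved, so the check is a comparison of the texts.

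**Step 1. Cross the subject's report with the investigator's judgment, for dissociation.**

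| Subject reports | Investigator judges | Section 3 | Section 4.5 | Agree? |
|---|---|---|---|---|
| none | none | may leave | may leave | yes |
| none | dissociative | may leave | stays until resolved | **no** |
| symptoms | none | release condition not met | no explicit rule for this mismatch | unclear |
| symptoms | dissociative | release condition not met | stays until resolved | yes |

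The direct contradiction is in the second row.

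**Step 2. Decide which text reflects the sponsor's intent.** Four places govern release or extended stay:

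1. Section 3: the subject's report.
2. Section 4.5, observation paragraph: the investigator's judgment of dissociation.
3. Section 4.5, paragraph on driving and impairment: the investigators, expressly not the subjects.
4. Section 4.5, risk-minimization paragraph: clinical judgment.

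Three of the four rest on investigator or clinical judgment, and only Section 3 rests on the subject. The third item concerns driving and hospitalization after named symptoms, so for discharge in general it supports this reading by analogy. The count shows intent; it does not measure risk.

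**Step 3. See how much of the second row is settled elsewhere.** The driving and impairment paragraph says whose judgment counts for the five symptom types it names. Compared with the Dissociation grouping in SAP Section 7.1.1:

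- feeling drunk: listed;
- visual disturbances: visual impairment, blurred vision and diplopia are listed;
- hallucinations: listed;
- dizziness: not listed;
- euphoric mood: not listed.

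So 3 of the 5 overlap with what the SAP counts as dissociation. That grouping is an analysis list, used here only to show the overlap. The paragraph does not name dissociation, depersonalization or derealization. Severe dissociation is also covered by the hospitalization rule. What remains is non-severe dissociation of those unnamed kinds, which the subject denies and the investigator detects.

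**Step 4. Suicidal symptoms.** No contradiction is claimed. For moderate to severe symptoms Section 4.5 only permits a longer stay. For mild symptoms it allows release on judgment with company arranged. Section 3 omits that route but does not oppose a mandatory rule to stay.

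**Step 5. How often the rule is applied.** Table 8-1 shows six infusion days (1, 8, 15, 22, 29 and 36). With about 66 subjects, 66 × 6 = 396, so there are at most about 396 release decisions. That counts decisions, not errors. Section 4.3 gives dissociative effects in 20–30% of ketamine subjects, but as an incidence, not as the share still affected at release. On persistence, Section 4.5 says of ketamine impairments that "none persisted longer than 2 hours after the beginning of the infusions", and release is no earlier than 2 hours. The corresponding duration under MIJ821 is not visible. The number of subjects in the second row therefore cannot be computed.

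**The case against.** The strongest reply is that Section 3 is a design overview. It shortens the Section 4.5 release sentence and differs from it by one verb (reports instead of have). Section 4.5 then adds the specific, mandatory qualifier, and a specific rule normally prevails over a summary. Section 3 does not forbid investigator judgment, and being allowed to leave is a permission, not an order to release. Section 14.1 also expects investigators to take any immediate action that safety requires, and the Site Operations Manual, which is not visible, may contain the working release procedure.

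Much of this stands as to weight. It explains why most sites would probably act correctly, and it keeps the point minor. It does not remove the inconsistency. Section 3 still states an operative criterion under which the report is enough, without a pointer to the stricter rule. The general safety clause is a fallback, and a manual that accompanies the protocol cannot cure a contradiction inside it. The word have in Section 4.5 and its hospitalization rule for severe symptoms confirm that Section 3 is the sentence out of line.

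It is also fair to say that sending a subject who reports symptoms but is judged to have none to Section 4.5 leads to no explicit rule. That gap exists now, and the proposed change does not widen it.

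**Conclusion.** The concern holds. Sections 3 and 4.5 conflict for a subject who denies symptoms but is judged dissociative, and Section 3 gives the less protective answer. The conclusion rests on the protocol text alone and needs no numerical assumption.

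The point is minor. The case is probably infrequent, sites would probably follow Section 4.5, and no endpoint or arm comparison is affected. Two things remain unknown: how long dissociation lasts under MIJ821, and what the Site Operations Manual says about release. Either could change the practical risk, but not the inconsistency in the protocol.

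**What to change.** Replace the release sentence in Section 3 with wording such as:

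> A subject may leave after the observation period when the subject's own report and the investigator's judgment are both negative for dissociative and for suicidal symptoms. In all other cases Section 4.5 governs release and extended stay.

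This keeps the self-report condition, adds the investigator's, and sends the conflicting case to the rule that already covers it. The accompanied-release route for mild suicidal symptoms is untouched. If the sponsor also wants to settle the case of reported symptoms that the investigator does not confirm, the place to do so is Section 4.5.

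The cost is one sentence at the next amendment and a short clarification to sites. An occasional subject may stay longer, but Section 4.5 already requires that stay. No assessment is added.
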